9.5.2 BASELINE EXAMS AND QUESTIONNAIRES

After the subject has signed the informed consent form and agreed to participate in the study, the exams, tests and questionnaires listed in the Baseline column of Table 2 should be performed. Refer to Appendix A for instructions for performing the exams and administering the questionnaire.

At this visit, subjects should undergo the following tests and exams, performed in the order indicated below, to screen them for the study qualification and to record baseline data. Endpoint assessments (indicated with a *) should be performed by independent study staff who does not perform the TearCare procedure on study subjects.

1. OSDI Questionnaire
2. Demographics, medical and ocular history
3. Medication use: ocular and systemic
4. Best-spectacle corrected visual acuity*
5. Slit Lamp Exam*
6. Tear Breakup Time*
7. Corneal staining*
8. Conjunctival staining*
9. Meibomian Gland Secretion Scoring*

If, at any point during the visit the subjects fails to meet a subject selection criterion, then the visit can be terminated. Subjects who fail to meet all the selection criteria will be considered a screen failure and will be withdrawn from the study. Screen failures will not count toward the total enrolled and treated number of subjects.

NOTE: Questionnaire and exam data collected on subjects prior to enrollment as part of the routine clinical practice may be used to pre-screen patients for the study. However, once the subject signs the consent form and is enrolled in the study, these questionnaires and exams must be repeated following the protocol procedures.

After all required measurements have been obtained and it has been confirmed that the subject meets all the Subject Selection Criteria, then the subject will receive the TearCare procedure.

9.5.3 TEARCARE PROCEDURE

The TearCare procedure should be performed by a clinician who did not perform the Baseline endpoint assessments. Refer to the TearCare Instructions for Use for detailed instructions for operating the TearCare System.

1. Obtain a new set of iLid devices and a TearCare SmartHub with enough battery left for at least one procedure.
2. Wipe the subject's eyelids and temple with the makeup removal wipe provided by the Sponsor. Allow the skin to dry or pad dry with a tissue. Use care not to allow any of the wipe to get into the eye.
3. Place a pair of iLid devices on the subject's eyelids and affix the temple housing to the subject's temple. Use the clip to secure the cables behind the subject's head.
4. Connect the iLid devices to the SmartHub.
5. Inform the subject that the iLid devices will heat up very quickly once the TearCare procedure is started.

6. Start TearCare procedure. Subjects should be encouraged to keep their eyes open and blink naturally during the TearCare procedure.
7. If the subject indicates the temperature is too hot, decrease the temperature set point to a setting that is comfortable for the subject.
8. Following the thermal portion of the TearCare treatment, remove the iLid devices from the subject and position the subject at the slit lamp to perform expression of the meibomian glands. Begin performing expression within 3 minutes of completion of the thermal portion of the procedure.
9. Apply 1 drop of proparacaine or tetracaine into each eye. Apply Akten® (lidocaine hydrochloride ophthalmic gel) 3.5% or equivalent into the lower eyelid fornices.
10. Using the Express Forceps, express the meibomian glands in all 4 eyelids using the following technique:
 - a. Think of each eyelid as having 3 zones: nasal, central & temporal.
 - b. For each zone, start at the fornix and work your way up to the margin.
 - c. Position the forceps horizontal, parallel to the margin.
 - d. Apply moderate continuous pressure and adjust based on the gland output.
 - e. Perform a second pass on the same eyelid to further express the glands.
 - f. After treating the lower and upper eyelids, repeat expression on all 4 lids to ensure complete expression.
 - g. Should the subject experience discomfort, it is reasonable to apply additional topical anesthetic.
 - h. The goal is to express each zone until the meibum coming out is clear.

Typically, complete expression takes approximately 5 minutes/eye.

9.5.4 MANAGEMENT OF DRY EYE SYMPTOMS DURING FOLLOW-UP

During follow-up, if subjects require relief of their dry eye symptoms, they should only use Refresh® Plus drops. Other types of over-the-counter lubricants should not be used. Subjects should record their daily use of lubricants on the Lubricant Drop log.

Subjects **should not use** any other method of relieving dry eye symptoms, including any of the following:

- Warm compress
- Restasis or Xiidra
- Other dry eye treatments (e.g. Lipiflow, TrueTear, iLux, punctal plugs, etc.)
- Lubricants other than Refresh Plus

NOTE: If a subject had a punctal plug at the baseline visit and it falls out during the study, it should be replaced.

Review these instructions with subjects at the end of the Baseline visit and provide them with the Lubricant Drop log. They should complete the log each day and bring it back to the clinic at the 1 month follow-up visit.

9.6 FOLLOW-UP VISITS

Prior to the Visit: Reminder Call

Since dry eye drops and lubricants can affect the endpoint assessments, it is important to call subjects a few days before their follow-up visits to remind them that on the day of the Follow-up visit, they should not to use any of these products before the Follow-up visit.

Order of Procedures During the Follow-Up Visit

Follow-up exams should not be performed by the clinician who performed the TearCare procedure.

Follow-up procedures will be performed per the Study Schedule provided in Table 2 (page 25) and the methods included in Appendix A. Since certain tests/exams can impact the ability to perform other tests/exams, the following tests and exams should be performed in this order:

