7 STUDY DESIGN

This is a prospective, single-arm, exploratory treatment study. This is a post-market study intended to collect clinical data regarding the safety and effectiveness of the TearCare System. To reduce potential bias in the study, study staff performing the endpoint assessments will be independent of the clinician performing the TearCare procedure.

In this study, all subjects will receive the TearCare procedure. The TearCare procedure includes an in-office 15 minute treatment session with the TearCare System immediately (i.e. within 3 minutes) followed by manual expression of the meibomian glands using the Express Forceps. Subjects will receive one in-office TearCare procedure at the baseline visit and will then have follow-up visits at 1 week and 1 month.

This study will be conducted at 2-3 sites in the United States.

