9 STUDY PROCEDURES

9.1 STUDY SCHEDULE

The Study Schedule is shown below in Table 2.

Table 2: Study Visit Schedule

Visit (Visit Window)	Baseline (Day 0)	Wk 1 (Day 5-9)	1 Mo (Day 21 – 35)
Informed Consent	X		
Demographics, Ocular & Medical History	X		
Medication use	X	X	X
OSDI*	X	X	X
Best Spectacle corrected visual acuity (Snellen)*	X	X	X
Slit Lamp Exam*	X	X	X
Tear Breakup Time*	X	X	X
Corneal Staining*	X	X	X
Conjunctival Staining*	X	X	X
Meibomian Gland Secretion Scoring*	X	X	X
TearCare Treatment	X		
AE Assessment*	X	X	X
Lubricant Drops Log			X

* Endpoint assessment should be performed by an independent study staff who does not perform the TearCare procedure on study subjects.

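### Sections 9.5.3 and 9.6 state assessor independence more weakly than Table 2 and 9.5.2, and nothing keeps earlier scores from the person grading the signs at follow-up

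*Combined protocol and SAP*

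**What the plan says.** The protocol states who may assess endpoints in five places.

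- Section 7 (Study Design): "To reduce potential bias in the study, study staff performing the endpoint assessments will be independent of the clinician performing the TearCare procedure".
- Section 9.1, Table 2 footnote, attached to the starred rows at Baseline, Week 1 and 1 Month: "Endpoint assessment should be performed by an independent study staff who does not perform the TearCare procedure on study subjects".
- Section 9.5.2 (Baseline exams), on the starred assessments: "should be performed by independent study staff who does not perform the TearCare procedure on study subjects".
- Section 9.5.3 (TearCare procedure): "The TearCare procedure should be performed by a clinician who did not perform the Baseline endpoint assessments".
- Section 9.6 (Follow-up visits): "Follow-up exams should not be performed by the clinician who performed the TearCare procedure". The next paragraph of 9.6 links back to the schedule: "Follow-up procedures will be performed per the Study Schedule provided in Table 2 (page 25)".

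On access to earlier scores the protocol is silent. Section 14.3 says that the study worksheets are the source data and are kept at the site in the subject or medical records. Neither section 9.6, section 14 nor Appendix A says whether a follow-up assessor may look at them before grading.

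**The concern.** Every effectiveness endpoint in section 6.1 is a mean change from baseline. The primary endpoint, tear break-up time (TBUT), is a stopwatch reading of when the examiner first sees a dry spot (20.4). Staining (20.5, 20.6) and gland secretion (20.7) are graded by eye. An examiner who expects improvement, and who has just read the subject's Baseline value, can be drawn toward a better follow-up grade without intending it. In a single-arm study that drift goes straight into the reported change.

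Assessor independence is the one step the protocol itself describes as reducing bias. It should therefore read the same wherever site staff meet it, and it should cover what the assessor can see as well as who the assessor is.

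**Working it through.** The plan gives no figure to reproduce, so the check is a comparison of texts.

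**1. Strength of the independence rule**

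| Place | Who is barred from assessing | Level |
|---|---|---|
| Table 2 footnote (9.1) | Anyone who treats study subjects | Role |
| 9.5.2 | Anyone who treats study subjects | Role |
| 9.5.3 | Treating clinician must not have done the Baseline assessments | Most naturally, per subject |
| 9.6 | The clinician who did the procedure | Most naturally, per subject |
| 7 | The clinician doing the procedure | Fits either reading |

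Suppose two clinicians at a site both treat. If each grades the other's subjects at follow-up, the explicit sentence in 9.6 is met and the Table 2 footnote is not. If neither grades anyone, both are met. So 9.6 is weaker than Table 2, not opposed to it.

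**2. Which rule governs follow-up.** Table 2 stars OSDI, visual acuity, slit lamp, TBUT, both stainings, gland scoring and adverse event assessment, each marked at Week 1 and 1 Month. Section 9.6 runs follow-up by that table, so the role-level rule formally applies. Under every reading, a clinician is barred from grading follow-up exams on a subject he or she treated.

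**3. Access to earlier scores.** Sections 9.6, 14 to 14.3 and 20.1 to 20.7 contain no rule that withholds them. Nor does anything bar the same person from grading at all three visits.

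**4. Which endpoints are exposed.** The OSDI is self-administered and staff may not make suggestive comments (20.1), so it falls outside the point. TBUT, the two staining scores and the gland score remain. Improvement is upward for TBUT and gland score and downward for staining.

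**5. What an assessor knows anyway.** Eligibility (8.1) already reveals that Baseline TBUT was at most 7 s in both eyes and the gland score at most 15 of 45 in each eye. Withholding the sheets hides the subject's own value within those limits. Staining has no entry limit, so there it hides the whole value.

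**6. Size.** The documents hold nothing from which an anchoring shift can be estimated. For scale only, the following shifts are assumptions with no source in the documents, set against the pilot changes in Table 1 of section 5.2:

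- TBUT: pilot change 14.8 − 3.1 = 11.7 s. An assumed shift of 0.5 to 1 s is 0.5/11.7 = 4% to 1/11.7 = 9% of it.
- Gland score: pilot change 41.0 − 6.3 = 34.7 points. An assumed 0.1 to 0.3 grade per gland gives 15 × 0.1 = 1.5 to 15 × 0.3 = 4.5 points, or 4% to 13% of it.

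**The case against.** Three stronger readings are tempting, and the documents do not support them.

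- *Treating clinicians may grade their own results.* No reading allows this. Even the weaker reading, grading another clinician's subjects, requires 9.6 to be read without the table it invokes, and assumes two treating clinicians at one site, which no section states.
- *Independence is the study's only bias control.* It is the only step given that label. The protocol also has a self-administered OSDI, the mean of three TBUT readings (20.4), a set instrument, hold time and scale for gland grading (20.7), and a fixed test order (9.5.2, 9.6).
- *Follow-up grades are made with Baseline values in view.* Section 14.3 says where worksheets are stored, not that they are at hand during grading. The gap is a missing rule, not a described practice.

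It is also fair to say that the study is exploratory, with no hypothesis (12.1), no pass/fail criteria (12.3) and descriptive statistics only (12.7). Every assessor knows that a follow-up visit comes after treatment. Holding back all earlier sheets would do harm too. Section 20.4 asks for the Baseline fluorescein method to be repeated where possible, and adverse event assessment needs Baseline data to judge increased severity (section 10) and acuity loss (10.2).

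These arguments stand. They lower the priority of the point and limit what should be withheld. They do not supply the missing rule, and they do not explain why the section that staff will follow at a follow-up visit carries the weaker sentence.

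**Conclusion.** The point holds in a limited form, as a cheap improvement rather than an error. Sections 9.5.3 and 9.6 state a weaker independence rule than Table 2 and 9.5.2. Because 9.6 invokes Table 2, aligning the wording mainly removes ambiguity. The more useful part is the second: nothing keeps earlier TBUT, staining and gland scores from the follow-up assessor, so these endpoints are open to anchoring that may bias change from baseline toward improvement, with no control arm to reveal it.

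The size is not estimable from the documents. The conclusion rests on two assumptions: that the protocol's silence leaves sites free to let assessors consult earlier sheets, and that examiner-judged signs respond to knowledge of earlier values.

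**What to change.** In 9.5.3 and 9.6, use the Table 2 rule: endpoint assessments are made by staff who do not perform TearCare on study subjects. Then add to 9.6:

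*At Week 1 and 1 Month, TBUT, staining and Meibomian Gland Secretion scores are recorded on a new worksheet before the assessor sees scores for these measures from earlier visits. The fluorescein method used at Baseline is carried forward on the new worksheet, and earlier data are released before the adverse event assessment.*

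This fits the order already set in 9.6, where adverse events come after gland scoring.

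The cost is a few sentences, a separate worksheet per visit, and a coordinator who holds back the earlier sheets until grading is done. No extra reader, visit or subject is needed, and staffing is no stricter than Table 2 already requires. The limits are that an assessor who also graded at an earlier visit may remember the score, and that treatment remains unmasked.

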1. OSDI
2. Best spectacle-corrected visual acuity
3. Slit Lamp Exam
4. Tear Breakup Time
5. Corneal staining
6. Conjunctival staining
7. Meibomian Gland Secretion Scoring
8. Assessment of adverse events

The following activities can be performed in any order:

- Medication Use
- Collection of Lubricant Drop Log (1 month visit only)

9.7 WITHDRAWAL AND DISCONTINUATION

All subjects have the right to withdraw at any point during the treatment without prejudice. The investigator can discontinue any subject at any time if continued participation in the study would result in harm to the subject. All efforts should be

made by the investigator to retain the subject in the study. If a subject withdraws prematurely from the study, a genuine effort must be made to determine the reason(s) the subject discontinued the study. The reason must be recorded in the subject's file and on the Study Exit Form.

10 ADVERSE EVENTS (AEs)

Adverse Events are defined below. Adverse events that occur in the eye during the trial, whether they are considered to be device related or not, must be documented in the subject's records. Date of the event, its severity, treatment (if any) and the assessed relationship of the event to the study device will be recorded on the Adverse Event Form. Conditions which exist at the time the subject is enrolled do not need to be recorded as adverse events unless they increase in severity during the study.

10.1 DEFINITIONS OF AE, SAE, SADE, USADE

Adverse Event	Any untoward medical occurrence in a subject who has been treated with the device that does not necessarily have causal relationship with the treatment.
Adverse Device Effect	Any unfavorable and unintended sign (including an abnormal laboratory finding), symptom, or disease that is possibly related to the study device.
Serious Adverse Event (SAE)	Any untoward medical occurrence that: 
• Results in death• Is life-threatening• Requires in-patient hospitalization or prolongs existing hospitalization• Necessitates medical or surgical intervention to preclude permanent impairment of a body function or permanent damage to a body structure• Sight threatening
Unanticipated Adverse Device Effect	Any serious adverse effect on health or safety, any life-threatening problem or death caused by, or associated with a device if that effect, problem, or death was not previously identified in nature, severity, or degree of incidence in the clinical investigational plan; or any other serious problem associated with a device that relates to the rights, safety, or welfare of subjects (21 CFR 812.3(s)). Any sight-threatening

	event, whether listed in the protocol or not, is considered to be reportable as a UADE
--	--

10.2 LIST OF ANTICIPATED POTENTIAL ADVERSE EVENTS

Anticipated potential adverse events include those that might reasonably be expected to occur in this study because they are associated with dry eye disease, the risk analysis for TearCare System (albeit remote likelihood), study testing methods or potential risks associated with warm compresses and lid massage.

- Burn, erythema, or swelling of the eyelids
- Conjunctival injection (Moderate or severe)
- Conjunctival abrasion
- Corneal abrasion
- Corneal deformation
- Allergic or inflammatory reaction to medical adhesive on the iLid device
- Formation of a chalazion or stye
- Loss in BSCVA of 2 lines or greater from baseline BSCVA
- Increased discomfort or pain of ocular surface (grittiness, foreign body sensation, etc.)
- Discomfort or pain of eyelids or orbit: Transient discomfort or pain during the TearCare procedure is not considered an adverse event. Persistent pain or discomfort may represent an adverse event, if judged so by the investigator.

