6.2 SAFETY ENDPOINTS

Safety will be assessed by evaluating the following measures over time:

- Device-related adverse events (all adverse events will be recorded)
- Best spectacle-corrected visual acuity (Snellen)

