10.3 REPORTING ADVERSE EVENTS AND UNANTICIPATED ADVERSE DEVICE EFFECTS

Identification, collection and reporting of adverse event information is the responsibility of the principal investigator. The investigator records the date of the event, its severity, treatment (if any) and the assessed relationship of the event to the study device on the Adverse Event Case Report Form (AE CRF).

Any ocular-related **serious adverse event** (SAE) should be reported to the study sponsor within one working day of learning of the event. Non-ocular-related SAEs should be

reported to the study sponsor within two working days of learning of the event. Email the AE CRF to [REDACTED].

Any **unanticipated adverse device effects (UADE)** must be reported to the following two entities:

1. The study sponsor – Within one working day of the investigator first learning of the event, e-mail the AE CRF to [REDACTED]; and
2. The reviewing IRB – As soon as possible, but no later than 10 working days after the investigator first learns of the event, report per the IRB's instructions.

The sponsor will conduct an evaluation of unanticipated adverse device effects. If the sponsor determines that an unanticipated adverse device effect presents an unreasonable risk to subjects, parts of the investigation presenting risks will be terminated. Termination will occur no later than 5 working days after the sponsor makes such a determination and no later than 15 working days after the sponsor first received notice of the effect.

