11.6 STEPS THAT WILL BE TAKEN TO CONTROL OR MITIGATE THE RISKS

The major risks to the subjects and the steps taken to control or mitigate them are described below:

1. Overheating of the eyelids: All TearCare treatments will be done in the investigator's office under direct supervision of the investigator. The device delivers heat to the eyelids at a temperature ranging from 41-45°C. This temperature range was selected because it is both safe for eyelid heating and effective for melting obstructions in the meibomian glands.^{24,25,26,27} The user can adjust the temperature up or down to a level that is comfortable, and may also shut off the System at any time if it is too uncomfortable or painful. In addition, the TearCare System continuously monitors and regulates the temperature at the tissue-contacting surface of the iLid devices and has been designed to not exceed the maximum allowable temperature.
2. Corneal abrasion: If the iLid devices are not positioned properly or come loose during the treatment, there is the potential for a corneal abrasion. To mitigate this, the supervising physician will apply the strips to the subject and will monitor their position during the treatment to ensure they remain in place and secure.

In addition, there is the possibility of corneal abrasion or abrasion of the eyelid surface during expression of the meibomian glands. To reduce the chance of abrasion, the forceps have been designed with smooth surfaces (i.e. no rough edges) and only trained users will perform expression.

²⁴ Lane SS, DuBiner H, Epstein RJ, et al. A New System, the LipiFlow, for the Treatment of Meibomian Gland Dysfunction. *Cornea*. 2012; 31 : 396-404

²⁵ Blackie CA, Solomon JD, Greiner JV, Holmes M, Korb DR. Inner Eyelid Surface Temperature as a Function of Warm Compress Methodology. *Optom Vis Sci* 2008;85:675-683.

²⁶ Moritz AR, Henriques FC. Studies of thermal injury: the relative importance of time and surface temperature in the causation of cutaneous burns. *Am J Pathol* 1947;23:695-720.

²⁷ Medical electrical equipment Part 1: General requirements for basic safety and essential performance (IEC 60601-1).

3. Worsening of dry eye symptoms: It is possible that subjects will experience a worsening of dry eye symptoms during the study. Subjects will undergo a complete eye exam at each visit and if any untoward or worsening signs of ocular surface disease are observed, they will be treated appropriately.

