12.4 EVALUABILITY

All subjects on whom the TearCare device is attempted will be considered evaluable for the safety analysis. All eyes that have at least one follow-up visit and have no major protocol deviations will be evaluable for the per protocol analysis.

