18.3.3 INVESTIGATOR RECORDS

A participating Investigator shall maintain the following accurate, complete, and current records relating to the Investigator's participation in an investigation for the period specified in Section 14.4:

1. All correspondence with another Investigator, an IRB, the Sponsor, a monitor, or FDA, including required reports.
2. Records of each subject's case history and exposure to the device. Case histories include the study CRF's/worksheets and supporting data including, for example, signed and dated consent forms and medical records. Such records shall include:
 - a) Documents evidencing informed consent.

- b) All relevant observations, including records concerning adverse device effects (whether anticipated or unanticipated), information and data on the condition of each subject upon entering, and during the course of, the investigation, including information about relevant previous medical history and the results of all diagnostic tests.
- 3. The protocol, with documents showing the dates and reasons for each deviation from the protocol.
- 4. Any other records that FDA requires to be maintained by regulation or by specific requirement for a category of investigations or a particular investigation.

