18.3.4 INVESTIGATOR REPORTS

An Investigator shall prepare and submit the following complete, accurate, and timely reports:

- 1. Unanticipated Adverse Device Effects - An Investigator shall submit to the Sponsor and to the reviewing IRB a report of any unanticipated adverse device effect occurring during an investigation as soon as possible, but in no event later than 10 working days after the Investigator first learns of the effect.
- 2. Withdrawal of IRB Approval - An Investigator shall report to the Sponsor, within 5 working days, a withdrawal of approval by the reviewing IRB of the Investigator's part of an investigation.
- 3. Progress - An Investigator shall submit progress reports on the investigation to the Sponsor, the monitor, and the reviewing IRB at regular intervals, but in no event less often than yearly.
- 4. Deviations from the Investigational Plan - An Investigator shall document and report to the Sponsor any deviation from the investigational plan.
- 5. Informed Consent - If an Investigator enrolls a subject without obtaining informed consent, the Investigator shall report such use to the Sponsor and the reviewing IRB within 5 working days after the use occurs.
- 6. Final Report - An Investigator shall, within 3 months after termination or completion of the investigation or the Investigator's part of the investigation, submit a final report to the Sponsor and the reviewing IRB.
- 7. Other - An Investigator shall, upon request by a reviewing IRB or FDA, provide accurate, complete, and current information about any aspect of the investigation.

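### Section 10.2 makes no exception for pain that ends treatment, so an early stop for transient eyelid or orbit pain may appear in no planned safety result

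*Combined protocol and SAP*

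**What the plan says.** Section 10.2 lists the anticipated adverse events. Its entry for eyelid or orbit pain carries a carve-out: "Transient discomfort or pain during the TearCare procedure is not considered an adverse event". The sentence that follows is the only limit on it: "Persistent pain or discomfort may represent an adverse event, if judged so by the investigator". Section 7 defines the procedure as the 15-minute heat session plus manual expression, so the carve-out covers both parts.

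Section 11.6, on overheating, foresees that a heat session may be ended for pain: the user "may also shut off the System at any time if it is too uncomfortable or painful". Section 9.5.3 lets the clinician lower the set point during heating and add topical anesthetic during expression. It does not ask for either to be recorded as an adverse event.

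Section 6.2 names two safety endpoints, Snellen best spectacle-corrected visual acuity and "Device-related adverse events (all adverse events will be recorded"). Section 12.4 sets the denominator: "All subjects on whom the TearCare device is attempted will be considered evaluable for the safety analysis". Section 12.7 limits the analysis to basic descriptive statistics, and section 12.3 sets no pass/fail criteria.

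**The concern.** Safety is half of the stated objective (section 2). A treatment that had to be stopped because the subject could not bear it is safety information, even if the pain is gone minutes later. The rule in 10.2 sorts procedural pain by duration and not by consequence. Brief discomfort relieved by a lower set point and brief pain that ended the session are treated alike, and neither is an adverse event.

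The plan names no tolerability, pain or procedure-completion measure that would pick up the second case. At stake is the completeness of the safety description. A report could state the number of device-related adverse events among all subjects attempted without showing that some of those subjects did not complete the procedure because of pain.

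**Working it through.** The plan gives no figure for early stops, and section 12.2 says no sample size was calculated, so there is nothing to reproduce. The check follows one subject through the text.

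**The case.** The heat session or expression is stopped for eyelid or orbit pain. The pain settles, and there is no burn, erythema, swelling, abrasion, moderate or severe conjunctival injection, or ocular-surface pain. All of those are listed separately in 10.2 without the carve-out.

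1. *Adverse event?* On the specific rule in 10.2, no. The pain was transient and occurred during the procedure, and the persistence clause does not apply.
2. *In the safety denominator?* Yes, because the device was attempted (12.4).
3. *In a planned safety result?* Not in the adverse event endpoint (step 1). Visual acuity (6.2) would be summarized for this subject but does not show the stop.
4. *Recorded elsewhere?* Possibly:
   - as a protocol deviation, on the form in section 15 and under 18.3.4: "An Investigator shall document and report to the Sponsor any deviation from the investigational plan";
   - in the exposure records of 18.3.3, which also cover "records concerning adverse device effects (whether anticipated or unanticipated");
   - in the subject's file and on the Study Exit Form, if the subject withdraws (9.7).
5. *Does any of these reach a planned output?* Only the last. Section 12.6 promises accounting by visit with dropout reasons, so a subject who stops and leaves the study would appear there. A subject who stops and stays would not. Section 16 covers product failure or malfunction, not pain.

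**Size.** The input from the documents is n = 30, the maximum in section 9.2. The per-subject stop rate p is an assumption. It covers only stops for transient eyelid or orbit pain with no other listed sign, and subjects are taken as independent.

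- Share of the safety denominator per stop: 1/30 = 3.3%.
- Expected stops: 30p.
- Chance of at least one: 1 − (1 − p)^30.

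| Assumed p | Expected stops | Chance of at least one | Added to AE count under 10.2 |
|---|---|---|---|
| 0% | 0 | 0% | 0 |
| 1% | 0.3 | 26.0% | 0 |
| 5% | 1.5 | 78.5% | 0 |
| 10% | 3.0 | 95.8% | 0 |

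The table shows what each assumed rate would imply. It is not evidence that stops occur.

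**The case against.** The strongest reply is that the carve-out is deliberate and sensible. Warming the lids and squeezing them with forceps can be expected to hurt briefly. The plan provides set-point reduction and anesthetic, and it refers persistent pain to the investigator. To be missed, an event must be confined to the eyelid or orbit, bad enough to end treatment despite those measures, fully transient, and free of every other listed sign. This stands: the gap is narrow, and the routine exclusion should stay.

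A second reply is that the definitions in 10.1 are broad. An adverse event is any untoward medical occurrence in a treated subject, and an investigator could record an aborted procedure on that basis. This stands in part. The specific sentence in 10.2 points the other way, so the two sections are in tension, and the 2-3 sites could code the same event differently.

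A third is that nothing suggests such stops happen. The shut-off sentence in 11.6 describes a safeguard. The 15-subject validation testing (5.1) and the 12 TearCare subjects in the pilot (5.2) had no reported adverse events. It is fair that no rate can be inferred. Those results do not show a zero rate either: the adverse event rules used are not given, and the pilot heated for 12 minutes where this study heats for 15.

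Finally, the end of expression is loosely set in 9.5.3, where the goal is clear meibum and the time is only typical. A rule about stopping before completion therefore needs an operational definition. This stands, and the fix supplies one.

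**Conclusion.** The point holds in a limited form. On the specific 10.2 rule, a subject who stops for transient eyelid or orbit pain, recovers with no other listed sign and stays in the study is in the safety denominator while the stop is in no planned safety result. If the subject also leaves the study, the stop can appear only in dropout accounting. Each such stop is 3.3% of 30 subjects. The frequency is unknown and may be zero. No test, pass/fail decision or effectiveness estimate is shown to change. This is a minor improvement to the safety description.

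A reader might infer more, and the documents do not support it:

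- *That stops for pain would go unrecorded.* Deviation, exposure and exit records may hold them, and the procedure worksheet, which is not among the documents, may already ask for the reason. The gap is in planned safety reporting.
- *That procedural harm in general is excluded.* The carve-out is confined to the eyelid and orbit entry.
- *That stops are likely.* The rates above are assumed.
- *That such a subject would also drop out of the effectiveness analysis.* That depends on an incomplete procedure being classed as a major deviation, which 12.4 and 12.5 do not settle.

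The conclusion assumes that the specific sentence in 10.2 governs over the general definitions in 10.1.

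**What to change.** Keep the exclusion for expected transient discomfort, including discomfort managed by lowering the set point within 41-45°C or by extra topical anesthetic. Then make two changes.

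1. **Safety results.** Report the number and percentage of subjects, over all on whom the device was attempted, whose heat session ended before 15 minutes because of pain, or whose expression was abandoned because of pain before the passes in 9.5.3 step 10 were done on all four lids.
2. **Section 10.2.** Add a sentence such as: *Pain that causes the heat session or the expression to be stopped early, as defined for the safety results, is not covered by this exclusion and is assessed by the investigator as an adverse event, with severity and relationship to the device.* Section 10.3 already has the investigator record severity and "the assessed relationship of the event to the study device", so no new assessment is created.

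The cost is one sentence, one descriptive line and, if the worksheet does not already capture an early stop and its reason, one field. The downside is a possibly slightly higher adverse event count.
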